9.5. Study Size

This is a descriptive study, and no comparative analyses will be conducted. Thus, the purpose of the sample size calculations provided below is to describe the expected precision of the estimates.

The following formula, based on the normal approximation to the binomial proportion, was used to calculate the sample size for this study:

$$n = \frac{P \cdot (1 - P) \cdot \left(Z_{1 - \alpha/2}\right)^2}{e^2},$$

Where P is the expected proportion of patients with evidence of having performed the recommended RMMs prior to/during treatment with ritlecitinib; e is the margin of error, or half the desired width of the CI; and $Z_{1-\alpha/2}$ is the standard normal Z-score corresponding to a cumulative probability of $1-\alpha/2$.

The proportion of patients with evidence of having performed the recommended RMMs prior to/during treatment with ritlecitinib (*p*) is not known in advance. Assuming varying proportions, the associated sample size and specified margins of error are provided in Table 2.

Table 2. Required Number of Ritlecitinib Treated Patients by Proportion of Patients With Evidence of Having Performed the Recommended Risk Minimization Measures (RMMs) and 95% Confidence Interval (CI) Width

Proportion of patients with evidence of having performed the recommended RMMs	Width of 95% CI (%)	Required number of patients
25%	10.0	289
	15.0	129
	20.0	73
50%	10.0	385
	15.0	171
	20.0	97
75%	10.0	289
	15.0	129
	20.0	73

Abbreviations: CI = confidence interval; RMM(s) = risk minimization measure(s).

The proportion of 50% yields the most conservative (i.e., the largest) sample size for a specified margin of error. In Table 2, a *minimum* sample size of 385 patients per database would maximize the precision of estimates. With 385 patients, the width of the CI will decrease as the proportion of patients with evidence of having performed the recommended RMMs approaches the extremes (0% and 100%, Table 3).

Table 3. Width of 95% Confidence Interval for a Range of Proportions, Assuming 385 Enrolled Patients

Proportion of patients with evidence of having	Width of
performed the recommended RMMs	95% CI (%)
10%	6.0
20%	8.0
30%	9.2
40%	9.8
50%	10.0
60%	9.8
70%	9.1
80%	8.0
90%	6.0

Abbreviations: CI = confidence interval; RMM(s) = risk minimization measure(s).

The study will include all patients identified during the study period who meet the eligibility criteria to maximize the precision of the estimates.

9.6. Data Management

All source data will originate via existing data collection practices of the data custodians in Denmark, France, and Sweden. Linkage across different data banks (e.g., registries) within a database (e.g., Danish registries) will be implemented either by a country investigator or by a data custodian, in accordance with the country-specific practices and rules. The investigators in each country will use the source data to create the analytic dataset.

Details on data management will be provided in the SAP. Briefly, data accruing in the routine databases undergo database-specific quality control, subject to data custodians' internal process in each country, which, as a rule, is a government agency (National Health Data Board in Denmark, SNDS in France, National Board of Health in Sweden). Databases in all three countries have been recently characterized in a EMA-commissioned study titled Strengthening Use of Real-World Data in Medicines Development: Metadata for Data Discoverability and Study Replicability (EUPAS39322, (44)). This study was part of the EMA Big Data Initiative. The specific steps of data management taken by investigators to define the analytic dataset from the source data will vary by country. Generally, this will entail the following main steps:

- Obtaining approvals and completing protocol-specific data applications.
- Retrieval of or access to the protocol-specific source data. Retrieval or access is administered by an appropriate data authority in each country.
- Data management to prepare the analysis dataset according to specifications in the SAP by transforming the original routinely collected data to coded data in order to define analysis populations and study variables.

- Data cleaning and checking for consistency by plausibility ranges, units of measurement, and relevance of clinical information. Implausible values will be set to missing. Imputation of missing values is not planned.
- Generation of aggregate-level country-specific SAP-specified output in a computer readable format according to the data template prepared at the principal investigator institution.

The principal investigator institution (Aarhus University) will use the country-specific aggregate data supplied via the data template (using Microsoft Excel or similar standard software) to generate output as appropriate per planned Tables, Listings and Figures, which will be specified in the SAP. The investigators will use either SAS or R software, in the most recent version available to their organizations at the time of the analyses.

9.7. Data Analysis

This is a descriptive study and the data will be analysed and results presented separately by country. Counts and proportions for categorical variables and mean and median with ranges for continuous variables will be calculated to address the study objectives, as below. All proportions will be reported with 95% CIs.

Data sources vary in collection of laboratory test and vaccine information (data on both laboratory tests and their results are available in Denmark; data on performed laboratory tests, but not results, are available in France; laboratory data are not available in Sweden). Data on vaccines are not available in Sweden.

Counts and proportions will be calculated for:

- 1. Patients with evidence of having performed the following laboratory tests and screenings within 3 months before index date:
 - Lymphocyte count
 - Platelet count
 - Screening for TB
 - Screening for viral hepatitis B and C
- 2. Patients with evidence of having performed the following laboratory tests at week 4 (\pm 2 weeks) after index date:
 - Lymphocyte count
 - Platelet count

- 3. Patients with evidence of having received live attenuated vaccines within 4 weeks before index date
- 4. Patients with evidence of having received live attenuated vaccines during treatment with ritlecitinib
- 5. Females in whom pregnancy, as recorded in the available data sources, overlaps with ritlecitinib use
- 6. Patients aged <12 years on the index date
- 7. Patients with a serious infection before index date
- 8. Patients with evidence of having measured risk factors and the number of measured risk factors for thromboembolic events within 12 months before index date
- 9. Patients with evidence of having measured risk factors and the number of risk factors for malignancy within 12 months before index date
- 10. Patients with evidence of having measured risk factors and the number of risk factors for CVD within 6 months before index date

The windows for ascertainment of presence of specific events may be revised to reflect the local data flow.

Detailed methodology for summary and statistical analyses of data collected in this study will be documented in a SAP, which will be dated, filed, and maintained by the sponsor. The SAP may modify the plans outlined in the protocol; any major modifications of primary endpoint definitions or their analyses would be reflected in a protocol amendment.

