Study design This is a descriptive drug utilization study using secondary data from healthcare databases in Denmark, France, and Sweden. These countries have universal healthcare.

Population The study population will include patients identified in each data source with a record of treatment with ritlecitinib from 15 September 2023 through 14 September 2028. Patients will not be required to have a recorded diagnosis of AA.

Variables The study will collect relevant data including patient demographics, comorbidities, prescription medications, vaccine administrations, and laboratory testing prior to the initiation of ritlecitinib and during treatment with ritlecitinib to address the study objectives.

Data sources This study will utilize routinely collected electronic healthcare data from national or regional population-based electronic healthcare registers in Denmark, France, and Sweden.

Study size All patients initiating ritlecitinib during the study period will be included.

Data analysis Data will be analysed in each country separately using a common protocol, database-specific definitions of the study variables, and a common analysis strategy. The main measures will be proportions of ritlecitinib users with a given indicator of RMM adherence.

Milestones Data collection will start in September 2027 and end in September 2030. Results will be summarized in a September 2028 interim report and a March 2031 final report.

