8.2. Study Objectives

The study objectives are to:

- 1. Evaluate, to the extent measurable in the available routinely collected data, indicators of HCP's adherence to the risk minimization measures (RMMs) in accordance with the ritlecitinib SmPC, HCP guide, and Patient Card, specifically:
 - Performing laboratory tests of lymphocyte count, platelet count, hepatitis B/C, and tuberculosis (TB) screening prior to initiation of ritlecitinib treatment
 - Performing laboratory tests of lymphocyte count and platelet count at week 4 (± 2 weeks) from initiation of ritlecitinib treatment
 - Avoiding live attenuated vaccines shortly before and during treatment with ritlecitinib
 - No use during pregnancy
 - No use in patients aged < 12 years
 - No use during serious infections
- 2. Describe the characteristics of patients before initiation of ritlecitinib treatment, in terms of:
 - Risk factors for thromboembolic events (including deep vein thrombosis (DVT), pulmonary embolism (PE), and arterial thrombosis)
 - Risk factors for malignancy
 - Risk factors for cardiovascular disease (CVD)

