9.1.2. Index Date

The date of the first dispensing or administration of ritlecitinib during the study period will be the index date.

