9.2.1. Inclusion Criteria

Patients must meet all of the following inclusion criteria to be eligible for inclusion in the study:

- 1. Have at least one dispensing of ritlecitinib during the study period
- 2. Have at least 12 months of continuous history in a participating data source before the index date

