9.3. Variables

Variables will include patient demographics (age and sex), comorbidities (measured by diagnoses from specialist health care at hospital encounters or treatment proxies), medication dispensings, procedures, and laboratory tests (Denmark and France only) prior to initiating ritlecitinib and monitoring tests during follow-up after treatment initiation. The maximum

lookback period for ascertaining characteristics before ritlecitinib initiation will be 12 months (365 days), but will vary for a given RMM measure, per SmPC.

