9.3.2. Indicators of Adherence to RMMs

The RMMs are described in the Risk Management Plan (13). Briefly, the RMMs recommend performing laboratory screening tests prior to ritlecitinib initiation, including lymphocyte count, platelet count, hepatitis B/C, and TB; performing laboratory tests of lymphocyte count and platelet count 4 weeks after initiation, avoiding live attenuated vaccines shortly before and during treatment, and avoiding use in pregnancy and during serious infections. Ritlecitinib is currently only indicated for those age 12 years or older.

- Lymphocyte count
- Platelet count
- Screening for TB
- Screening for viral hepatitis B and C
- Live attenuated vaccines
 - o Measles
 - o Mumps
 - o Rubella
 - Others as available in data sources
- Pregnancy
- Serious infections

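### TB and hepatitis B/C screening is counted only in the 3 months before first dispensing, so a low French proportion could not be split into earlier screening and no recorded screening

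*Protocol*

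**What the plan says.** The objective in Protocol 8.2 is "Performing laboratory tests of lymphocyte count, platelet count, hepatitis B/C, and tuberculosis (TB) screening prior to initiation of ritlecitinib treatment". Section 9.3.2 summarises the measures in the same way: "the RMMs recommend performing laboratory screening tests prior to ritlecitinib initiation, including lymphocyte count, platelet count, hepatitis B/C, and TB". Neither gives a time limit for the pre-treatment tests, although 9.3.2 does give timing for the later blood counts and for live vaccines.

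Section 9.3 sets an upper limit: the "lookback period for ascertaining characteristics before ritlecitinib initiation will be 12 months (365 days), but will vary for a given RMM measure, per SmPC". Section 9.7, item 1, then counts "Patients with evidence of having performed the following laboratory tests and screenings within 3 months before index date" and lists lymphocyte count, platelet count, TB screening and hepatitis B and C screening under that one window. No reason for 3 months is given.

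On timing and available history, 9.1.2 states that "The date of the first dispensing or administration of ritlecitinib during the study period will be the index date", and inclusion criterion 2 in 9.2.1 requires patients to "Have at least 12 months of continuous history in a participating data source before the index date".

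Table 1 lists TB and hepatitis screening as available in France only, as a test record without a result. The single sensitivity analysis (9.7.1) restricts to patients with an alopecia areata diagnosis and leaves the screening window unchanged.

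**The concern.** The Abstract says that "The main measures will be proportions of ritlecitinib users with a given indicator of RMM adherence". For TB and hepatitis B/C, the numerator is limited to tests in the 3 months before first dispensing, while the denominator is all eligible users. A patient screened 3 to 12 months before index was screened before treatment began, which is what the objective asks, and that interval lies inside the history required of every patient. Under item 1 this patient cannot be told apart from one with no recorded screen.

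What is at stake is how a low figure would be read. Section 7 says that the results will help to show whether the risk minimisation programme met its aims or needs amending. Earlier screening and absent screening have different implications for that decision. France is the only source for these two indicators, so no other country's result could help to separate them.

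**Working it through.** **Inputs from the Protocol.** Window of 3 months (9.7, item 1); required history of at least 12 months (9.2.1); index at first dispensing or administration (9.1.2); TB and hepatitis data in France only (Table 1); planning minimum of 385 patients per database (9.5).

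**The plan's own figure.** Section 9.5 uses n = P(1 − P)z²/e². With P = 0.50, z = 1.96 and e = 0.05, n = 384.15, rounded up to 385. This matches Table 2, and the other eight entries of Table 2 also reproduce. The point does not dispute any stated number.

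**What each window can show.** Sort all users by their most recent recorded test before index:

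- A: within 3 months
- B: 3 to 12 months before
- C: more than 12 months before
- D: no recorded test

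As proportions, A + B + C + D = 1. The planned indicator is A, and its complement is B + C + D. A 12-month indicator is A + B, and its complement is C + D. With both reported, the difference (A + B) − A = B is the share screened only in the earlier interval. The planned output cannot give B. Group C stays mixed with D under either window.

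**Illustration of size.** Let P = A + B + C be the proportion with any recorded screen before initiation, and f = (B + C)/P the share of those whose latest screen was more than 3 months before index. The planned indicator then reports P(1 − f), a shortfall of P × f against the time-unlimited objective. The Protocol gives neither P nor f. Taking P = 80%, f from 5% to 40% and n = 385, all as assumptions:

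| f | Reported | Shortfall (points) | 95% CI |
|---|---|---|---|
| 0% | 80.0% | 0 | 76.0 to 84.0 |
| 5% | 76.0% | 4 | 71.7 to 80.3 |
| 10% | 72.0% | 8 | 67.5 to 76.5 |
| 20% | 64.0% | 16 | 59.2 to 68.8 |
| 40% | 48.0% | 32 | 43.0 to 53.0 |

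The intervals are reported ± 1.96 × √(reported × (1 − reported)/385). For example, 0.72 ± 1.96 × √(0.72 × 0.28/385) = 0.72 ± 0.045. In this example the interval excludes 80% from f = 10% upward; at f = 5% it does not. A larger sample narrows the interval without changing the shortfall. A 12-month window recovers only the part of f that belongs to group B.

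**The case against.** The case for leaving the plan alone is substantial, and most of it stands.

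- **No contradiction.** A reader might infer that 9.7 breaks 9.3. It does not: 3 months is under the 12-month ceiling, 9.7 does use different windows for different items, and 9.3 does not require infection screening to have a different window from blood counts. Giving an open-ended objective a time limit in the analysis section is ordinary operationalisation.
- **The SmPC.** Section 9.3 ties the windows to it, and it is not at hand, so it may support 3 months. How long a TB or hepatitis screen stays relevant is not settled in the Protocol.
- **The opposite bias.** The research question is prescribers' adherence to the ritlecitinib recommendations. Section 9.4.2 says that the French data hold no indication, so a test ten months earlier cannot be tied to the decision to start ritlecitinib. Crediting it could overstate adherence. This defeats any proposal to make 12 months the main window.
- **Index date.** The measures are framed around initiation, and first dispensing is a natural anchor for that. The Protocol does not show that prescribing-decision dates are available in France, so the choice of anchor is not a fault.
- **Labelling.** The Protocol counts patients with evidence of testing. It nowhere calls the remainder non-adherent.
- **Room for change.** Section 9.7 says that "The windows for ascertainment of presence of specific events may be revised to reflect the local data flow", the SAP may modify the plan, and 9.3.7 leaves refined country definitions to the SAP. Section 9.9 admits difficulty in identifying TB and hepatitis screening.

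The last item softens the point without answering it. The revision clause concerns data flow, and 9.9 does not mention the window. None of these objections bears on a second proportion reported beside the first.

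**Conclusion.** The point holds as a limit on what can be read from the result. The 3-month window is permissible, but it is narrower than the objective and unexplained. Used alone, it leaves a low French proportion open to two readings, earlier screening or no recorded screening, and no planned analysis separates them. The effect is confined to two indicators in one country.

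Relative to the time-unlimited objective, any discrepancy from the window can only be downward. Its size is unknown: the 4 to 32 points shown above follow entirely from the assumed 80% and the assumed f of 5% to 40%, and 385 is a planning minimum, not a forecast of the French sample. A reader might go further and conclude that the study will materially understate adherence, or that 3 months is the wrong window. The documents support neither conclusion. They do not say how many users were screened earlier or how old a screen may be.

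**What to change.** Keep the 3-month proportion in 9.7, item 1, as planned for all four tests. In 9.7 or 9.7.1 add, for TB screening and for hepatitis B/C screening in France, the proportion with a test within 12 months before index, with its 95% CI, reported beside the 3-month figure. State that the 12-month figure is an upper companion to the 3-month figure and not a replacement, because it may include tests done for other reasons. State also that screens more than 12 months before index are still not counted.

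The cost is about one line of protocol text and one extra column for two French indicators. No additional history is needed, because inclusion criterion 2 already guarantees 12 months. This is a measurement window only and takes no position on how old a screen may be in practice.

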8. RESEARCH QUESTION AND OBJECTIVES

8.1. Research Question

The research question is: to what extent do routinely collected data indicate health care professional's (HCP) adherence to the recommendations for the use of ritlecitinib described in the Summary of Product Characteristics (SmPC), HCP guide, and Patient Card?

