9.3.1. Exposure

The date of the first dispensing of ritlecitinib during the study period will be the index date. The exposure will continue until the end of a 90-day grace period following the estimated discontinuation of the index treatment. Duration of each dispensing will be computed based on days supplied, estimated based on assumed daily dose, package size, and number of packages in each dispensing. Only the first continuous treatment episode will be considered in this study.

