- The ability to ascertain whether the recommended screenings or monitoring took place is limited when using automated health databases because many of the recommendations are at the discretion of the HCP and/or because they will not be captured in administrative claims or register data. For example, it is not possible to assess whether the physician ensured that the woman was using effective contraception or was not lactating. Additionally, it will not be possible to robustly assess whether HCPs discontinued ritlecitinib in response to a patient developing an infection because, for some infections, it will be challenging to assess severity and, depending on the length of the drug holiday, the databases might not capture a discontinuation in response to an infection (e.g., if it was shorter than the anticipated duration of the prescription). Therefore, the screening and monitoring recommendations proposed for assessment in the current study represent only those which can be objectively captured in automated health databases, such as laboratory tests for key clinical values. Furthermore, in data sources in which ritlecitinib use cannot be ascertained in hospital settings, lack of use during serious infectious cannot be assessed.
- Finally, while a subset of risk factors for thromboembolic events, malignancy, and CVD can be assessed in administrative data, it is not possible to confirm whether the prescribing HCP considered the risks and benefits before initiating ritlecitinib in patients at high risk for these outcomes. Thus, an assessment of risk factors can be used to characterize the exposed population but not confirm whether the recommended screening guidelines were considered. Data on body mass index, diet, and exercise are not captured in the participating data sources and data related to smoking and alcohol use is limited and must be inferred by proxies (e.g., tobaccoand alcohol-related conditions).

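### The pregnancy indicator (Section 9.7, item 5) pools three situations in one overlap count, so a high value cannot be attributed to prescriber behaviour

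*Protocol*

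**What the plan says.** The research question in Section 8.1 is "to what extent do routinely collected data indicate health care professional's (HCP) adherence to the recommendations for the use of ritlecitinib". Section 8.2 lists "No use during pregnancy" among the adherence indicators. Its only planned measure is item 5 of Section 9.7: "Females in whom pregnancy, as recorded in the available data sources, overlaps with ritlecitinib use".

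Section 9.3.1 defines use. On supply it states: "Duration of each dispensing will be computed based on days supplied, estimated based on assumed daily dose, package size, and number of packages". Then: "The exposure will continue until the end of a 90-day grace period following the estimated discontinuation of the index treatment". Also: "Only the first continuous treatment episode will be considered in this study".

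No other part of the protocol separates the situations that item 5 combines:

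- Pregnancy as a thromboembolic risk factor (Section 9.3.3) uses the 12 months up to and including the index date, so it mixes pregnancies already ended with current ones.
- The sensitivity analysis in Section 9.7.1 restricts to patients with an alopecia areata diagnosis.
- The Annex 2 checklist marks stratified analyses and exposure time windows as not applicable.
- Section 9.9 acknowledges incomplete pregnancy capture and adds that "it is not possible to assess whether the physician ensured that the woman was using effective contraception or was not lactating". It discusses the difficulty of seeing a stop in response to an event for infection only.

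**The concern.** By its definition, item 5 gives the same score to three different histories:

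- (a) pregnancy already in progress on the index date;
- (b) conception after index, with at least one further dispensing once the pregnancy is on record;
- (c) conception during estimated supply, or in the 90 days after it, with no further dispensing.

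Groups (a) and (b) bear more closely on whether the recommendation was followed. A woman in (c) may have stopped as soon as the pregnancy was known. If she conceived in the grace period, she may have had no estimated supply left.

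Group (a) is fixed at initiation, while (c) accumulates with time on drug. The pooled proportion can therefore rise with treatment duration alone. The study is meant to inform whether the risk minimisation programme needs amending (Section 7), and a raised value would not show what needs amending.

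The protocol already makes this kind of distinction for vaccines, with item 3 before index and item 4 during treatment.

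**Working it through.** **The plan's own figure.** Item 5 has no expected value. The nearest figure is the precision target in Section 9.5: 0.50 × 0.50 × 1.96² / 0.05² = 384.2, rounded up to 385, which reproduces Table 2. It concerns precision, not what item 5 measures, and the point does not depend on it.

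**Step 1: bound.** Let A, B and C be the numbers of females in (a), (b) and (c), and N the females in the denominator. Item 5 = (A + B + C)/N ≥ (A + B)/N. If item 5 reads 1%, at most 1% can be in (a) or (b) among recorded pregnancies. If it reads 7.7%, (a) and (b) together can be anything from 0% to 7.7%.

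**Step 2: growth with time on drug.** Assumptions, none from the protocol: a proportion q pregnant at index; a constant conception rate r per woman-year; mean estimated supply T years, unaffected by conception. The grace period is 90/365.25 = 0.246 years (Section 9.3.1).

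Item 5 ≈ q + (1 − q) × r × (T + 0.246)

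With q = 1% and r = 3 per 100 woman-years, (1 − q) × r = 0.0297:

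| T (years) | (b) + (c) | Item 5 | Share pregnant at index |
|---|---|---|---|
| 0.5 | 0.0297 × 0.746 = 2.22% | 3.22% | 1/3.22 = 31% |
| 1 | 0.0297 × 1.246 = 3.70% | 4.70% | 1/4.70 = 21% |
| 2 | 0.0297 × 2.246 = 6.67% | 7.67% | 1/7.67 = 13% |

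Prescribing at initiation is identical in all three rows.

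**Step 3: range.** At T = 1 year, with r from 1 to 5 per 100 woman-years and q from 0% to 1%, item 5 runs from 1.25% (0.01 × 1.246) to 7.2% (1% + 0.99 × 5% × 1.246). The share pregnant at index runs from 0% to 45%. With nobody pregnant at index, item 5 still reads 1.25% to 6.2%. If none of those women was dispensed again, that is all (c).

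**Step 4: grace period.** With a constant rate, the share of post-index conceptions that fall after estimated supply has ended is 90/(T + 90), T in days: 33% for T = 180, 20% for 365 and 11% for 730.

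**Limit of the illustration.** It separates (a) from (b) + (c). It does not show how (b) and (c) divide; nothing in the protocol gives a basis for that.

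**The case against.** The strongest reply is that item 5 measures the recommendation as written. Recorded overlap is the direct reading of no use in pregnancy, Section 8.2 claims only indicators to the extent measurable, and refined definitions go to the SAP (Section 9.3.7), which could add the split. That stands as far as it goes: the count is legitimate and should be kept. But the protocol itself fixes a single overlap count as the adherence measure, and dividing it changes how the result can be read.

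The split does not reveal intent either. A pregnancy in progress at index may have been unknown to the prescriber, and a dispensing is a pharmacy event. This is accepted. Nor is (c) wholly irrelevant to the programme, since Section 9.9 gives contraception as a recommendation the data cannot show and a conception on treatment may bear on it.

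Feasibility is also a fair objection. The French codes in Table 1 are mainly for deliveries, terminations and ectopic pregnancies, so onset must be estimated, and a three-way split is more sensitive to dating error than a simple overlap. Section 9.10 masks counts of 1 to 4 and any count from which they could be recomputed. At an assumed 1%, (a) needs 500 females to reach 5 cases; with 200 it would be 2, and masked.

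Three stronger readings are tempting and not supported:

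- A low pooled value might be thought to hide initiations in pregnancy. It cannot among recorded pregnancies in the first episode, because those initiations are part of the count.
- Item 5 might be thought unable to answer the objective at all. A low value does inform it.
- The pooling might be thought to distort a comparison between countries. Section 9.7 reports countries separately and Section 9.5 plans no comparative analyses.

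**Conclusion.** The point holds in a limited form. Item 5 is informative when low and ambiguous when high, because conceptions with no later dispensing score the same as starting or re-dispensing in a pregnancy and accumulate with time on drug. The 90-day grace period adds conceptions after estimated supply has ended.

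This structural point follows from Sections 9.3.1 and 9.7 alone. Its size is not known from the protocol: under the assumed rates, one-year values run from 1.25% to 7.2% with at most 45% of counted women pregnant at index, and those figures are illustrative only. This is a worthwhile, low-cost improvement to a stated measure, not an error that invalidates it.

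**What to change.** Keep the overall overlap count in item 5 and also report:

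- **5a:** pregnancy in progress on the index date;
- **5b:** conception after index with at least one ritlecitinib dispensing after the first pregnancy record or, where only the pregnancy end is recorded, after a pre-specified interval from estimated conception;
- **5c:** conception after index, within estimated use, with no such later dispensing.

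State in advance that 5a and 5b are the categories closer to HCP adherence, without implying that the prescriber knew of the pregnancy, and that 5c describes exposed pregnancy. Report 5b and 5c also per 100 woman-years, so that treatment duration does not drive the reading. Where cell sizes allow, note how many in 5c arise only in the grace period.

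The cost is wording in item 5 and the SAP, plus choosing the interval for 5b. The split otherwise uses the pregnancy and dispensing dates that the overlap already needs. 5a and 5b will be approximate in France. Where small cells and their complements are masked under Section 9.10, only the total is shown, and the report should then say that a high total cannot be attributed to prescribers.
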